### **6.9.1.2 Percent of Total Body Surface Area Affected by Atopic Dermatitis at Days 15, 29 and 57**

Change from Baseline in the percent of total BSA affected by AD at Days 15, 29, and 57 will be analyzed using ANCOVA with Baseline percent of total BSA affected by AD as covariate and treatment as factor.

Summary statistics will be presented for the percent of total BSA affected by AD and change from Baseline at each timepoint (Day 15, Day 29, Day 57 and Day 85).

### **6.9.1.3 Investigator Global Assessment at Days 15, 29 and 57**

The proportion of subjects with IGA success defined as an IGA score of Clear (0) or Almost Clear (1) with at least a 2-grade improvement from Baseline at Day 15, Day 29, and Day 57 will be analyzed using the same logistic regression method described for the primary endpoint.

Summary statistics by IGA Score at each timepoint (Baseline, Day 15, Day 29, Day 57 and Day 85) and dichotomized IGA at each post-Baseline timepoint (Day 15, Day 29, Day 57 and Day 85) will also be presented at each post-Baseline timepoint.

#### **6.9.1.4 Signs of Atopic Dermatitis at Target Lesions (at selected photography sites only) at Days 29, 57 and 85**

At selected sites, a target lesion will be identified, photographed and scored with the Signs of AD.

The change from Baseline to Day 29, and Day 57, and Day 85 Signs of AD total score at target lesions will be analyzed using an ANCOVA with Baseline score as a covariate and treatment as a factor.

Summary statistics for each of the Signs of AD scores (erythema, exudation, excoriation, induration/papulation, and lichenification) and total score at target lesions for each timepoint will be presented (Baseline, Day 15, Day 29, Day 57 and Day 85).

### **6.10 Sensitivity Analyses**

The sensitivity analyses will be performed using the ITT population.

#### **6.10.1 Repeated Measures**

The first sensitivity analysis for the primary endpoint, IGA success, will be analyzed using a repeated measures logistic regression (generalized estimating equations), with dichotomized IGA success as the dependent variable and treatment group, visit, and treatment group by visit interaction as independent factors. In this analysis, data from all post-Baseline visits will be included with no imputation for missing data.

```
proc genmod data = datain;
  class SUBJECT TRT VISIT;
  model IGA SUCCESS = TRT VISIT TRT * VISIT / dist=bin;
  repeated subject = SUBJECT/type = cs;
  lsmeans TRT*VISIT / diff;
  estimate 'pval' TRT 1 -1 TRT*VISIT 0 0 1 0 0 -1;
run;
```

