Efficacy will be assessed through collection of the IGA, Signs of AD score, BSA of AD, EASI score, and changes in pruritus. An IGA will be conducted at Screening to ensure subject eligibility and again at Baseline (if not same day as Screening Visit) and Days 15, 29, 57 and 85. The IGA assesses the overall status of the AD lesions at the time of the assessment. Every effort should be made to have the IGA conducted by the same investigator/sub-investigator at each visit. No comparisons are made to previous assessments. The IGA is scored from 0 (Clear) to 4 (Severe) based on scoring system provided in Table 2.

Table 2 Validated Investigator Global Assessment scale for Atopic Dermatitis (vIGA-ADTM)^a

Instructions:

The IGA score is selected using the descriptors below that best describe the overall appearance of the lesions at a given time point. It is not necessary that all characteristics under Morphological Description be present.

Score	Morphological Description
0 – Clear	No inflammatory signs of atopic dermatitis (no erythema, no induration/papulation, no lichenification, no oozing/crusting. Post-inflammatory hyperpigmentation and/or hypopigmentation may be present.
1 - Almost clear	Barely perceptible erythema, barely perceptible induration/papulation, and/or minimal lichenification. No oozing or crusting.
2 – Mild	Slight but definite erythema (pink), slight but definite induration/papulation, and/or slight but definite lichenification. No oozing or crusting.
3 – Moderate	Clearly perceptible erythema (dull red), clearly perceptible induration/papulation, and/or clearly perceptible lichenification. Oozing and crusting may be present.
4 – Severe	Marked erythema (deep or bright red), marked induration/papulation, and/or marked lichenification. Disease is widespread in extent. Oozing or crusting may be present.

Notes:

1. *In indeterminate cases, please use extent to differentiation between scores*

For example:

- *Patient with marked erythema (deep or bright red), marked papulation and/or marked lichenification that is limited in extent, will be considered “3 – Moderate”.*

2. *Excoriations should not be considered when assessing disease severity.*

^a Copyright ©2017 Eli Lilly and Company – Used with the permission of Eli Lilly and Company under a Creative Commons Attribution-NoDerivatives 4.0 International License – <https://creativecommons.org/licenses/by-nd/4.0/>

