## **6. STATISTICAL AND ANALYTICAL PLANS**

### **6.1 General Methodology**

All statistical processing will be performed using SAS® 9.4 or higher. No interim analyses are planned. This Phase 2 study is designed to identify the response of BTX 1204 4.0% BID compared to Vehicle BID. Statistical tests will be exploratory. No adjustments for Type I error will occur.

Descriptive statistics will be used to provide an overview of the efficacy and safety results. For categorical parameters, the number and percentage of subjects in each category will be presented. For continuous parameters, descriptive statistics will include n (number of subjects), mean, standard deviation (SD), median, minimum and maximum.

The primary method of handling missing efficacy data in the Intent-to-Treat (ITT) and modified Intent-to-Treat (mITT) analysis sets will be based on last observation carried forward (LOCF). Repeated measures analyses will be used on the observed data as a sensitivity analysis on the primary endpoint.

The efficacy analysis performed on the ITT population is considered the primary analysis. The efficacy analyses performed on the mITT and per-protocol (PP) populations are considered supportive analyses.

The number of subjects in each analysis set will be summarized. Reasons for study withdrawal during the study will be summarized using frequencies and percentages by treatment group.

Reported AEs, medical history terms and prior and concomitant procedures and therapies will be classified on the basis of Medical Dictionary for Regulatory Activities (MedDRA) terminology. Prior and concomitant medications will be classified on the basis of World Health Organization Drug Dictionary (WHO-DDE) terminology.

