Table 14.1.4.4: Summary of Concomitant Antibiotic Therapies by ATC Level 2 Term and Preferred Name (Safety Population)

**Programming note:** Replace 3rd footnote with - Percentages are based on the number of subjects in each treatment group in the Safety population.

Table 14.2.1.1: Primary Efficacy Endpoint: Dichotomized IGA Success at Day 85  
(ITT Population)

	BTX 1204 4% BID (N=xxx)	Vehicle BID (N=xxx)	Treatment P-Value a
At Least a 2 Grade Improvement from Baseline and IGA Grade of 0 or 1			
n	xx	xx	
Success	xx ( xx.x%)	xx ( xx.x%)	
Failure	xx ( xx.x%)	xx ( xx.x%)	
Success a	xx.x%	xx.x%	x.xxx
Failure a	xx.x%	xx.x%	

a Estimates and p-value from a logistic regression with a term for treatment group.

Note: Missing values imputed using LOCF.

SOURCE: USERNAME\SPONSOR\PROJECT\JOBNAME (DATE,TIME)

Repeat Table 14.2.1.1 for the following:

Table 14.2.1.2: Primary Efficacy Endpoint: Dichotomized IGA Success at Day 85 (mITT Population)

Table 14.2.1.3: Primary Efficacy Endpoint: Dichotomized IGA Success at Day 85 (PP Population)

**Programming note:** *Replace last footnote with* - Note: No imputations were made for missing data.

Table 14.2.1.4: Sensitivity Analysis of Primary Efficacy Endpoint: Dichotomized IGA Success at Day 85  
(ITT Population)

	BTX 1204 4% BID (N=xxx)	Vehicle BID (N=xxx)	Treatment P-Value a
At Least a 2 Grade Improvement from Baseline and IGA Grade of 0 or 1			
n	xx	xx	
Success	xx ( xx.x%)	xx ( xx.x%)	
Failure	xx ( xx.x%)	xx ( xx.x%)	
Success a	xx.x%	xx.x%	x.xxx
Failure a	xx.x%	xx.x%	

a Estimates and p-value from a repeated measures logistic regression with .factors of treatment group, visit and treatment group by visit interaction.

Note: No imputations were made for missing data.

SOURCE: USERNAME\SPONSOR\PROJECT\JOBNAME (DATE,TIME)

Table 14.2.1.6: Subgroup Summary of the Primary Endpoint: Dichotomized IGA Success at Day 85  
(mITT Population)  
(Page 1 of 5)

			Geographical Region: US	
			BTX 1204 4% BID (N=xxx)	Vehicle BID (N=xxx)
At Least a 2 Grade Improvement from Baseline and IGA Grade of 0 or 1				
n			xx	xx
Success			xx ( xx.x%)	xx ( xx.x%)
Failure			xx ( xx.x%)	xx ( xx.x%)
			Geographical Region: AUS/NZ	
			BTX 1204 4% BID (N=xxx)	Vehicle BID (N=xxx)
At Least a 2 Grade Improvement from Baseline and IGA Grade of 0 or 1				
n			xx	xx
Success			xx ( xx.x%)	xx ( xx.x%)
Failure			xx ( xx.x%)	xx ( xx.x%)

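### The ESTIMATE line in SAP 6.10.1 is written for three visits, but the model has four, so the contrast is non-estimable and cannot supply the Day 85 p-value

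*SAP*

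**What the plan says.** SAP 6.1 states that "Repeated measures analyses will be used on the observed data as a sensitivity analysis on the primary endpoint". SAP 6.10.1 gives the model: a GEE logistic regression of dichotomized IGA success on treatment, visit and treatment by visit, in which "data from all post-Baseline visits will be included with no imputation for missing data". The PROC GENMOD code lists TRT before VISIT in the CLASS statement and ends with two output statements: "lsmeans TRT*VISIT / diff", then "estimate 'pval' TRT 1 -1 TRT*VISIT 0 0 1 0 0 -1".

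The post-Baseline IGA visits are not in doubt. Protocol 6.1 schedules the IGA at Screening and "again at Baseline (if not same day as Screening Visit) and Days 15, 29, 57 and 85". SAP 6.9.1.3 lists the same four post-Baseline days for the dichotomized IGA.

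The result goes to Table 14.2.1.4, titled "Sensitivity Analysis of Primary Efficacy Endpoint: Dichotomized IGA Success at Day 85", which has space for one treatment p-value. Its footnote reads "Estimates and p-value from a repeated measures logistic regression with" the three model factors. It does not say which output statement supplies the p-value.

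**The concern.** The six interaction coefficients look like a last-visit contrast for a study with two arms and three post-Baseline visits. This study has four. If the line does not fit the model, the only statement in the code that isolates a single comparison, and the one labelled `pval`, cannot produce the Day 85 result that the table reports.

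The text of 6.10.1 gives the model but not the contrast, so the code is the only place in that section where the contrast is defined. If it fails, someone has to repair or replace it at the programming stage, although the SAP is meant to fix it in advance. A program that evaluated the line without checking estimability could also print a number for a different visit under a Day 85 title.

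**Working it through.** **Inputs.**
- Arms: 2 (SAP 4.1).
- Post-Baseline IGA visits: 4 (Protocol 6.1; SAP 6.9.1.3), all in the model (SAP 6.10.1).
- CLASS order: TRT, then VISIT, so VISIT varies fastest within TRT*VISIT.
- Coefficients as written: TRT (1, -1); VISIT none; TRT*VISIT (0, 0, 1, 0, 0, -1).

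**Parameter count.** Intercept 1 + TRT 2 + VISIT 4 + TRT*VISIT 2 x 4 = 8, giving 15 columns. There are 8 arm-by-visit cells, so the rank is 8. The line supplies 6 of the 8 interaction coefficients; the remaining two are taken as zero.

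**Where the coefficients fall.** Taking visits in time order:

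| | Day 15 | Day 29 | Day 57 | Day 85 |
|---|---|---|---|---|
| First arm | 0 | 0 | 1 | 0 |
| Second arm | 0 | -1 | 0 | 0 |

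**Estimability.** A row L is estimable only if it is a weighted sum of the cell rows. Each interaction column belongs to one cell, so the interaction coefficients are themselves the cell weights. Those weights then determine every other coefficient:
- Intercept: 1 - 1 = 0, as in the line.
- TRT: (1, -1), as in the line.
- VISIT: (0, -1, 1, 0) is required, but the line has (0, 0, 0, 0).

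The VISIT part does not match, so the contrast is not estimable.

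**Numerical confirmation.** The rows were tested against the over-parameterised design. The residual is the largest absolute departure of L from the row space; zero means estimable. It is a yes/no diagnostic and does not measure bias.

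| Contrast | Visits | Residual | Estimable |
|---|---|---|---|
| SAP line | 3 | 0 | Yes: third-visit difference |
| SAP line | 4 | 0.333 | No |
| SAP line, TRT varying fastest | 4 | 0.333 | No |
| SAP line, either column order | 5 (Baseline added) | 0.333 | No |
| 0 0 0 1 0 0 0 -1 | 4 | 0 | Yes: +1 and -1 on Day 85 only |

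Reordering the visit levels does not rescue the line. With four visits, the 3rd and 6th positions always fall on different visits.

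**What the line would return if evaluated anyway.** One GEE dataset was simulated with 100 subjects per arm, four visits and an exchangeable working correlation. The assumed success rates were 5, 12, 22 and 35% on BTX 1204 and 4, 8, 14 and 20% on vehicle. They are illustrative and do not come from the documents. The SAP line gave three different log-odds values, depending on how the redundant parameters were resolved:
- last levels set to zero: 0.279, which is the Day 57 difference;
- first levels set to zero: 0.747, which is the Day 29 difference;
- minimum norm: 0.726.

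The actual Day 85 difference was 0.690 (SE 0.319, p = 0.030). The eight-coefficient line returned 0.690 under all three solutions, identical to the Day 85 cell difference.

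**LSMEANS output.** Eight cell means give 8 x 7 / 2 = 28 pairwise differences. Four compare the arms at the same visit, and one of those is Day 85.

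**The case against.** The strongest reply is that the analysis is not lost. The LSMEANS statement directly above the faulty line outputs the Day 85 difference between arms with its p-value. The title of Table 14.2.1.4 fixes the visit and the population, so only one of the 28 differences can be meant, and any sensible repair gives the same number. The table also needs model-based success percentages for each arm, which a single contrast cannot provide. Reading both the percentages and the p-value from LSMEANS is therefore natural, and the footnote does not name the ESTIMATE line. In addition, the tests are exploratory with no Type I error adjustment (SAP 6.1.8), and Protocol 9.2 disclaims hypothesis testing.

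Much of this stands. The Day 85 result is recoverable, the link from the ESTIMATE line to the table is inferred from the label `pval`, and nothing in the documents shows that the repair would be made after unblinding. It limits the consequence but does not remove the error. The SAP contains a contrast that does not fit its own model, gives it the label that points to the reported p-value, and nowhere states that the LSMEANS difference is to be used instead.

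**Conclusion.** The concern holds. The line gives 6 interaction coefficients where 8 are needed, puts no interaction weight on Day 85 in either arm, and is not estimable with four visits. It is correct only for three visits with VISIT varying fastest. Placing the weights at Day 57 and Day 29 assumes that visits are sorted in time order; the non-estimability does not depend on that order or on the simulated rates.

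The effect is confined to one pre-specified sensitivity result. The primary LOCF logistic regression (SAP 6.8.1) and the tipping-point analysis (SAP 6.10.2) do not use this code. It should be corrected, but it does not threaten the trial's main conclusion.

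**What to change.** Before unblinding, make one of two changes.

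1. Replace the line with `estimate 'Day 85' TRT 1 -1 TRT*VISIT 0 0 0 1 0 0 0 -1;` and state that the VISIT levels are ordered Day 15, 29, 57, 85.
2. Delete the ESTIMATE line, and state in SAP 6.10.1 and in the Table 14.2.1.4 footnote that the p-value is the Day 85 BTX 1204 versus vehicle difference from the LSMEANS statement.

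Both give the same comparison. The cost is one line of code with its ordering note, or a short statement in those two places. No new data are needed and the primary analysis does not change.

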#### **6.10.2 Tipping Point**

A tipping point analysis of the primary endpoint, proportion of subjects with IGA success defined as an IGA score of Clear (0) or Almost Clear (1) with at least a 2-grade improvement from Baseline at Day 85, will be performed as a sensitivity analysis for the handling of missing data. Specifically, a range of response rates for both groups will be explored to determine the tipping point(s) at which the combinations result in no longer reaching statistical significance.

## 6.11 Safety Evaluation

### 6.11.1 Extent of Exposure

The extent of exposure to study drug in each treatment group will be summarized by total number of applications, number of missed applications, number and percentage of subjects who are compliant, and amount of drug used total. Exposure and compliance will not be calculated for subjects who are lost to follow-up. A subject will be considered compliant with the dosing regimen if the subject applies 80% to 120% of the expected number of applications while enrolled in the study.

The total amount of study drug used will be calculated from the drug accountability record using the recorded weights for subjects with an initial weight and return weight for all dispensed pumps of study drug. The difference between the dispensed weight and the returned weight for each pump will be summed over all pumps to calculate the total amount of study drug used.

Compliance will be calculated based on the applications of study drug. The total number of applications is as follows:

If 2 applications expected on Date of Last Application:  $2 * (\text{Date of Last Application} - \text{Date of First Application} + 1) - (\text{Number of doses marked as missed on the CRF})$ .

If 1 application expected on Date of Last Application:  $2 * (\text{Date of Last Application} - \text{Date of First Application}) + 1 - (\text{Number of doses marked as missed on the CRF})$ .

The total number of applications expected is as follows:

$2 * (\text{Date Subject Ended Participation} - \text{Date of Randomization} + 1)$ .

If the total number of applications exceeds 178 then it will set to 178.

Compliance will be calculated as a percentage as 100 times the total number of applications taken divided by the total number of applications expected while enrolled in the study.

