5.1.8. Duration of Therapy

Subjects will receive BID application of study drug for 84 days with a final application on the evening of Day 84 for a total of 168 doses. If the Day 85 Visit is delayed, the subject should continue dosing through the evening before the scheduled Day 85 Visit.

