5.2. Study Drug Accountability Procedures

At each study visit the clinical site will weigh each pump dispensed to the subject and returned from the subject to calculate the amount (grams) of study drug used. The investigator will keep a current and accurate inventory of all clinical supplies received. These records will be reviewed at each monitoring visit performed by the CRA per SOPs. In case of drug accountabilities discrepancies (missing pump, lost pump or non-compliance cases in which more product was used compared to expected use), investigators should obtain more information and explanation from the subjects.

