6.3.7. Day 85 Visit/End of Study Visit

The final application of study drug will occur on the evening prior to the Day 85 Visit. If the Day 85 visit is delayed, the subject should continue BID application until the evening before the Day 85 Visit. At the Day 85 Visit (Day 85 \pm 5 days), the following will be conducted:

- Collect and weigh returned study drug pumps
- Collect study diary
- Query subject for adverse events that occurred since the previous visit
- Query subject for changes in concomitant medications
- Collect blood sample for CBC and chemistry
- Collect urine sample for urinalysis
- Conduct UPT (WOCBP only)
- Perform IGA
- Calculate BSA of total AD involvement
- Assess Signs of AD score
- Collect EASI score
- Collect I-NRS
- Photographs and Signs of AD scoring of target lesion (selected sites only)
- Discharge subject from study

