### **6.4.5 Per-Protocol Population**

All subjects in the ITT population who complete the Day 85 visit without noteworthy study protocol violations will be included in the PP population and analyzed according to the treatment group received. The PP population will include subjects in the ITT population who do not meet any of the following criteria:

- Violated the inclusion/exclusion criteria;
- Have taken any interfering concomitant medication;
- Has missing IGA assessment at the Day 85 visit;
- Have missed both the Day 29 and Day 57 visits;
- Have not been compliant with the dosing regimen (i.e. subjects must apply 80 – 120% of the expected applications of study medication during participation in the study);
- Out of visit window at the Day 85 visit by  $\pm 7$  days;

Subjects that discontinue from the study due to an AE related to study treatment or documented lack of treatment effect will be included in the PP population. Prior to breaking the blind, other additional criteria may be added to the list to accommodate for unforeseen events that occurred during the conduct of the trial that result in noteworthy study protocol violations.

All efficacy analyses will be performed on the PP population with results considered as supportive.

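### SAP 6.11.1 counts two doses on the exit-visit day that the protocol does not schedule, and its 120% compliance limit cannot be reached within the visit window

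*SAP*

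**What the plan says.** Protocol 5.1.8 has subjects dose twice daily for 84 days, "with a final application on the evening of Day 84 for a total of 168 doses", and adds: "If the Day 85 Visit is delayed, the subject should continue dosing through the evening before the scheduled Day 85 Visit". Protocol 6.3.3 and 6.3.7 agree, and Table 4 schedules no in-clinic dose at the Day 85 visit, whose window is ±5 days.

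SAP 6.11.1 defines three quantities:

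- **Applications taken:** two per day from first to last application (one on the last day if only one was expected), minus doses marked missed on the CRF.
- **Applications expected:** 2 × (end of participation − randomization + 1).
- **Cap:** "If the total number of applications exceeds 178 then it will set to 178".

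Compliance is taken divided by expected, over the time enrolled, and the rule is "A subject will be considered compliant with the dosing regimen if the subject applies 80% to 120% of the expected number of applications". The same 80–120% range defines the per-protocol exclusion in SAP 6.4.5 ("Have not been compliant with the dosing regimen"). It also appears in the footnotes to Table 14.3.0.1 and Listing 16.2.5.3.

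**The concern.** The denominator includes the exit day, on which the protocol schedules no dose, so a subject who follows the protocol exactly is reported below 100%. The numerator has no term for extra applications, so the upper limit is stated as a criterion but cannot operate. This matters because Protocol 5.2 lists among accountability discrepancies "non-compliance cases in which more product was used compared to expected use". The denominator also runs to the end of participation rather than to the last dose, which lowers the score of anyone whose exit visit comes some days after stopping.

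At stake are the compliance results in Table 14.3.0.1 and one of the per-protocol criteria. Both are secondary to the ITT efficacy analysis.

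**Working it through.** **Inputs.** Randomization and first dose on Day 1. Last dose the evening before the final visit (Protocol 5.1.8, 6.3.3, 6.3.7). Final visit on Days 80 to 90 (6.3.7). Formulas from SAP 6.11.1. Write E for the exit day and X for the last day dosed.

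**1. The documents' own figures.** 2 × 84 = 168, as Protocol 5.1.8 states. The cap also reproduces: 2 × 89 = 178, which is dosing through the evening before a Day 90 visit.

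**2. Full adherence under the SAP formula.** Taken = 2 × (E − 1); expected = 2 × E.

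| Exit day | Taken | Expected | No cap | 178 caps taken | 178 caps expected |
|---|---|---|---|---|---|
| 80 | 158 | 160 | 98.8% | 98.8% | 98.8% |
| 85 | 168 | 170 | 98.8% | 98.8% | 98.8% |
| 90 | 178 | 180 | 98.9% | 98.9% | 100.0% |
| 92 | 182 | 184 | 98.9% | 96.7% | 102.2% |
| 108 | 214 | 216 | 99.1% | 82.4% | 120.2% |

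The excess is two doses at every exit up to Day 89. At Day 90 it disappears only if the cap applies to expected doses.

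**3. Effect on the 80% cut-off at Day 85.** 0.8 × 170 = 136. 0.8 × 168 = 134.4, so 135 in whole doses. A subject with 135 doses scores 135/170 = 79.4% under the SAP and 135/168 = 80.4% under the protocol's count. No other dose count changes class.

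**4. The 120% limit.** At Day 85 it needs more than 1.2 × 170 = 204 applications; a full doser is credited with 168. More generally, with first dose at randomization and last dose no later than exit, taken cannot exceed 2 × (E − 1 + 1), which is the uncapped expected number. Inside the window the ratio therefore never passes 100%. With the cap on expected doses alone it reaches 120% only at a Day 108 exit.

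**5. What 178 caps.** The wording of the cap sentence matches the SAP's name for doses taken, but the sentence follows the formula for doses expected. The table shows that the two readings give different results from Day 90 on.

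**6. Early discontinuers.** With no missed doses, compliance = 2X / 2E = X/E. It is at least 80% only if E − X ≤ X/4.

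- Exit the day after the last dose: 7/8 = 87.5%, 14/15 = 93.3%, 28/29 = 96.6%, 56/57 = 98.2%. All pass.
- Longer gaps: 14/17 = 82.4% passes, 14/18 = 77.8% fails; 28/35 = 80.0% passes, 28/36 = 77.8% fails; 56/70 = 80.0% passes, 56/71 = 78.9% fails.
- Very early stops with exit the next day: 1/2 = 50.0%, 2/3 = 66.7%, 3/4 = 75.0%. All fail.

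The reason for stopping does not enter the formula. The gap lengths are illustrative; the documents do not give any.

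**The case against.** The strongest reply is that very little turns on this. One dose count changes class, the upper limit is idle rather than harmful, and the ITT analysis does not use compliance. All of that stands.

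SAP 4.1 gives Day 84 as study exit, where the formula returns 168. That does not rescue it. If dosing ends the evening before the visit, a Day 84 exit gives 166 taken against 168 expected, the same excess of two. The Day 84 statement needs reconciling with Day 85 elsewhere in any case.

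A reader might infer that the formula marks adverse-event discontinuers as non-compliant and so removes people whom the per-protocol rule means to keep. The documents do not support that. The denominator stops at each subject's own exit, Protocol 4.3 ends enrollment and dosing together on withdrawal, and prompt exits pass except after about three days of dosing or fewer. SAP 6.4.5 also expressly includes discontinuers for related AEs or documented lack of effect. That sentence has effect only if it overrides the other criteria, since its opening requirement is completion of Day 85. Discontinuers for other reasons would usually be excluded for a missing Day 85 IGA whatever their compliance.

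A reader might also infer that over-use goes unseen. Protocol 5.2 concerns quantity of product, followed up through pump weights, and SAP 6.11.1 already summarises grams used. What is missing is only an over-use check within the compliance percentage.

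**Conclusion.** The point holds. The denominator disagrees with the protocol's dosing schedule by two doses, the 120% limit cannot operate within the visit window, and the target of the 178 cap is undefined. At a Day 85 exit the reported percentage for a full doser is 1.2 points too low (98.8% against 100%).

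It would go too far to say that a perfect user can never reach 100%: at Day 90 the score is 100.0% if the cap applies to expected doses.

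The gap between last dose and exit can put an early discontinuer below 80% in the compliance table. It does not decide per-protocol membership for the related-AE and lack-of-effect discontinuers whom SAP 6.4.5 keeps.

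These results assume that participation ends on the date of the final visit, that first dose and randomization fall on the same day, and, for the discontinuer figures, that no doses were missed before stopping.

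**What to change.** In SAP 6.11.1:

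- Set expected applications to 2 × (end of participation − randomization), leaving out the exit day. This gives 2 × 84 = 168 at Day 85 and 2 × 89 = 178 at Day 90, in line with the protocol and the cap.
- State whether 178 caps doses taken, doses expected or both. It still matters beyond Day 90. At Day 92, inside the ±7 days that SAP 6.4.5 allows, a full doser would have 182 of 182. Capping taken alone gives 178/182 = 97.8%; capping expected alone gives 182/178 = 102.2%.
- Either drop the 120% limit, here and in SAP 6.4.5 and the table and listing footnotes, and leave over-use to the pump-weight summary already planned, or add recorded extra applications to the numerator.
- Say how to treat a subject whose participation ends on the day of randomization (expected would be zero) and a dose applied on the exit day (169/168 = 100.6% at Day 85).

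Ending expected doses at permanent discontinuation is optional. It would replace the SAP's measure over time enrolled with adherence while on drug, so a subject who stopped on Day 10 but attended Day 85 could score 100%. Without it, the new denominator shortens the counted gap by one day but does not remove it.

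The denominator, the cap and dropping the limit are SAP text changes that can be made before unblinding, with no new data. Counting extra applications may cost more, since Listing 16.2.5.4 shows only missed doses.
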